# 4 Study Synopsis

Study title	The ADAPT study (Adapting, Disease self-management and							
	Acknowledgement through Psychosocial Targeted interventions)							
Short title	The ADAPT study							
Principal	[name] and [name]							
Investigators								
Chief Investigators'	University of Cambridge							
employing Institution								
Study sponsor	University of Cambridge							
Funder	LUPUS UK and The Lupus Trust							
	·							
Study Duration	3 years (over 2 phases)							
Participants								
Sample size	Phase 1							
	N=120 (n=30 in each of the 3 intervention groups of text messaging							
	intervention, listening support (The Wren Project) and the online physical							
	activity course (Flexifit Pilates) and n=30 in control.							
	Phase 2							
	N=800 (approximately)							
	Numbers dependent on which interventions progress to phase 2, and sample size calculations informed by phase 1. Provisional estimates of N=100 for online physical activity, N=100 for The Wren support, N= 300 for							
	text messaging support and N=300 control.							
	Process and acceptability evaluation interviews with phase 1 participants will take place until theoretical saturation (the point at which no new concepts are generated) is reached. Estimated 15 for each intervention group.							
Objectives	Aim							
	To assess the acceptability, feasibility and effectiveness of methods of remote psychosocial support for SARDs patients. For the interventions trialled (if effective and acceptable) to be incorporated as an adjunct to usual care.							
	Objectives							
	To trial multiple quality of life and mental health measures to determine the most appropriate primary and secondary outcomes for phase 2.							
	To test processes to inform phase 2 effectiveness trial.							
	To develop and trial our own ADAPT instrument to more accurately							

	reflect, measure and monitor SARD patient personal, social and medical satisfaction.  • To assess the acceptability (phase 1) and effectiveness (phase 2) of remote psychosocial interventions on the mental health, wellbeing, self-esteem, resilience, loneliness and disease acceptance of patients with systemic autoimmune rheumatic diseases.

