#### 6.2 Inclusion Criteria

Both phases - Aged 18 years and over

Phase 1: Any INSPIRE (Ethics reference: PRE2021.27) study participant reporting a diagnosis of SLE and requesting on the INSPIRE survey (completed Jul-Sep 23) to be considered for the ADAPT trial.

Phase 2: Reporting a diagnosis of any SARD.

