#### 6.3 Participant recruitment

For both the phases, patients who expressed an interest in participating in ADAPT at the end of the INSPIRE survey will be emailed with an ADAPT information sheet to confirm continued interest in participating in ADAPT. They will be randomly selected (until trial numbers filled) and then randomly allocated by the study statistician using block randomisation into one of the intervention or control groups. If INSPIRE study participant responses do not generate sufficient ADAPT participant numbers, additional recruitment will be through online advertising via patient charities and support groups and then randomly allocated to intervention groups. If numbers interested in phase 1 exceed study capacity, those participants will be emailed to be informed they were not randomly selected to

participate in phase 1 but will be invited to apply again for phase 2 if interested. Exact sample sizes for phase 2 will be calculated from phase 1 effectiveness result indications. Phase 1 participants will not be eligible for phase 2 participation.

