#### Follow-ups

Follow-up 1 - Baseline+ 12 weeks

Follow-up 2 - Baseline + 6 months

Participants will be sent up to 3 email reminders for non-response to the follow-up questionnaires.

#### 6.7 Selection of outcome measures for phase 2

Phase 2 primary and secondary outcome measures will be selected from the analysis of phase 1 quantitative and qualitative results. Following phase 1 analysis, the multidisciplinary ADAPT study team will meet to decide which intervention(s) will proceed to phase 2 and which outcome measures to select for phase 2. The selection criteria will include (with most weight given to patient views on importance):

- 1. Acceptability and perceived importance and relevance of each measure to patients. These will be assessed quantitively by questions on the survey about each instrument, and qualitatively during interviews. Any measures that are rated as unacceptable or irrelevant by >25% of participants will be excluded. Participants will be asked to rank the measures in terms of importance to them and a mean score calculated. The top 3 scoring outcome measures will be discussed, taking into account additional patient views from interviews, team views and sensitivity as detailed below to select one measure for the primary outcome measure. Other measures will be considered for inclusion as secondary outcomes, by considering the ordering of patient scores, and patient willingness to complete different lengths of follow-up surveys. A minimum of one phase 1 outcome measure will be excluded for phase 2.
- 2. Sensitivity of each measure to change by psychosocial interventions. Short-term effectiveness of each intervention will be measured by using the within-person change from baseline to follow-up one, for each phase 1 instrument.

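### Phase 2 is to be sized from phase 1 effectiveness results with 30 per arm, which are too imprecise for that purpose, and no target difference is stated

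*Protocol*

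**What the plan says.** Section 6.3 (Participant recruitment) gives the rule for sizing phase 2: "Exact sample sizes for phase 2 will be calculated from phase 1 effectiveness result indications". The synopsis is looser: "Numbers dependent on which interventions progress to phase 2, and sample size calculations informed by phase 1". It adds provisional figures, "Provisional estimates of N=100 for online physical activity, N=100 for The Wren support", with 300 for text messaging and 300 for control, about 800 in all.

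Phase 1 is "N=120 (n=30 in each of the 3 intervention groups", plus 30 controls.

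The section on selecting outcome measures for phase 2 defines the phase 1 effectiveness result: "Short-term effectiveness of each intervention will be measured by using the within-person change from baseline to follow-up one", for each instrument. The same section makes responsiveness in those data one of the inputs to the primary outcome. The three measures ranked highest by patients are discussed with interview findings, "team views and sensitivity as detailed below to select one measure for the primary outcome measure".

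The protocol gives no target difference, minimal important difference, SD, alpha, power, shrinkage or confidence-limit rule for phase 2.

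**The concern.** A target difference should be one that is worth detecting. If the estimate from a small pilot takes its place, the sampling error of the pilot passes into the size of the main trial, and because n varies with the inverse square of the effect, that error is magnified. A chance high estimate gives an effectiveness trial too small to find a worthwhile effect. A chance low one gives a size that cannot be recruited, or none at all. The nominal power written into phase 2 would then not be its real power.

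Two other rules in the protocol compound this. A within-person change contains time trend and regression to the mean as well as the intervention effect, so it is not the between-arm difference on which a controlled phase 2 must be sized. And if a measure is chosen partly because it moved a lot in phase 1, the effect carried forward tends to be too large. Phase 1 also enrols any "study participant reporting a diagnosis of SLE", whereas phase 2 is open to any systemic autoimmune rheumatic disease, so the phase 1 effect belongs to a narrower population.

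**Working it through.** **The plan's own figures.** The arms add up: 4 × 30 = 120, and 100 + 100 + 300 + 300 = 800. No power calculation can be reproduced, because none of its inputs is given.

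**Inputs.** From the protocol: 30 per arm in phase 1. Assumed, because the protocol is silent: two-sided alpha 0.05, 80% nominal power, 1:1 comparison, true standardised effect 0.3 to 0.5 SD, baseline to follow-up correlation 0 or 0.7, no loss to follow-up. Complete-case analysis, the protocol's primary option, can only lower the 30.

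**Step 1, precision of the phase 1 effect.**
- SE(d) = √(2/30 + d²/120). At d = 0.4: √(0.0667 + 0.0013) = 0.261.
- 95% range of the observed effect: 0.4 ± 1.96 × 0.261 = −0.11 to 0.91.
- With baseline adjustment, ignoring the small d² term: SE = √(2(1 − 0.7²)/30) = 0.184, half-width 0.36 SD.

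**Step 2, size per arm from an observed effect.**
- n = 2(1.96 + 0.8416)²/d² = 15.70/d².
- At the true 0.4: 98 (99 rounded up).
- At an observed 0.6: 44. At an observed 0.2: 392 (393 rounded up). At 0.1: 1,570.

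**Step 3, real power at the size chosen.**
- Power = Φ(d/√(2/n) − 1.96).
- True 0.4 with n = 28: Φ(1.50 − 1.96) = 32%.

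**Step 4, simulated pilots put through steps 2 and 3.** Results are for pilots with an observed standardised effect above 0.1. The rest give more than 1,570 per arm or no computable size.

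| True effect, correlation | Pilots excluded | n needed | Planned n, 10th–90th percentile | Mean real power | Trials under 60% power |
|---|---|---|---|---|---|
| 0.4 SD, none | about 12.5% | 98 | about 28 to 425 | 69% | 39% |
| 0.3 SD, none | 22% | 174 | about 35 to 593 | 63% | 49% |
| 0.4 SD, 0.7 | about 4% | 50 | about 19 to 212 | 74% | 30% |

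Across all pilots, none excluded:
- True 0.3 SD, no correlation: the planned n is under half of what is needed in 32%, and over double or not computable in 37%.
- True 0.5 SD, correlation 0.7 (a favourable case): 15% and 21%.

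**Step 5, what phase 1 can estimate.** The SD pooled over four arms has 120 − 4 = 116 degrees of freedom. Its 95% interval is about 0.89 to 1.15 times the estimate, which moves n by a factor of 0.79 to 1.32. Using the effect instead gives a 10th to 90th percentile spread of about 425/28 = 15-fold.

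**Step 6, the provisional numbers.** Taken as they stand:

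| Comparison | Power at 0.3 SD | Power at 0.4 SD | Difference detectable with 80% power |
|---|---|---|---|
| 100 v 300 | 74% | 93% | 0.32 SD |
| 300 v 300 | 96% | over 99% | 0.23 SD |

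These sizes would be respectable, but the synopsis makes them depend on the later calculation.

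**The case against.** The wording is loose. Talk of indications, and the synopsis's "sample size calculations informed by phase 1", could cover the SD as well as the effect. A reader might infer that the plan fixes a formula in which the observed difference becomes the target difference. It does not say that, and a later analysis plan could specify a sound calculation. This stands as a limit on certainty. But an effectiveness result most naturally means the observed effect, and nothing in the protocol points elsewhere.

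The provisional numbers might be thought to protect phase 2. If 100 per arm were a floor, power at 0.4 SD would be about 81% even for 100 v 100. The protocol does not make them a floor.

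The main simulation uses an unadjusted difference, while the analysis section foresees regression. Adjustment shrinks the problem, as the last row of the table shows, but does not remove it.

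Three stronger readings are not supported:
- That a poor pilot estimate would by itself cause a useful intervention to be abandoned. Section 6.1 bases progression on satisfaction, engagement and feasibility, with no effect size. The only route is indirect: a very large computed size judged infeasible.
- That the phase 1 interval is wider than any plausible effect. The protocol puts no bound on plausible effects.
- That choosing the outcome on responsiveness biases the estimate by a known or large amount. Patient views carry most weight, and the size of any bias is unknown.

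**Conclusion.** The point holds on the natural reading of section 6.3. Following the sentence as written would leave the real power of phase 2 largely to chance: with a true effect of 0.4 SD, mean power of about 69% against a nominal 80%, and 39% of trials below 60% (30% with a baseline correlation of 0.7). These rates rest on the assumed alpha, power, effect and correlation, and on leaving out pilots with an observed effect of 0.1 or less. They make no allowance for dropout, for the mismatch between within-person change and a between-arm contrast, or for selection of the outcome. Nothing in phase 1 depends on the sentence, so this is a should-fix, to be settled before phase 2 is sized.

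**What to change.** Replace the section 6.3 sentence with wording such as:

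> The phase 2 sample size will be based on a target difference for the chosen primary outcome that is judged important and is set independently of the effect observed in phase 1. Phase 1 will supply the SD (pooled over arms, with allowance for its uncertainty), the baseline to follow-up correlation and retention.

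Bring the synopsis into line. Treat clustering in group-delivered arms as an external assumption shown over a range: phase 1 has only two exercise groups of 15, which cannot usefully estimate it. For the ADAPT instrument, or any measure without an established important difference, state the target and justify it with patient and clinician input.

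The cost is protocol wording and the work of agreeing a target. The provisional 800 may move in either direction. For orientation, 1:1 at 80% power needs 393 per arm at 0.2 SD, 175 at 0.3, 99 at 0.4 and 63 at 0.5.

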#### 2. Listening support.

This will be provided by The Wren Project, in line with their standard programme of offering listening support (via Zoom) by a trained 'listener' (as opposed to counsellor) to patients with an autoimmune disease. Each Ppt will have fortnightly 50 minute one to one 'talking' sessions over 12 weeks. The focus will be talking about the impact of the disease and coping.

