#### Listening therapy

Several studies have assessed effectiveness of formal counselling and cognitive behavioural therapy (27) and mindfulness (28) in SLE. Outside of trials, these types of therapy are often prohibitively expensive to either the NHS or to the individual, making them unlikely to be cost-effective to include as part of SLE care, however effective and acceptable. One of our interventions will therefore be a charity run project, The Wren Project, that provides free listening support to patients with autoimmune diseases, and potentially represents a more sustainable cost-effective method of support. The listening support is provided by trained volunteers with the focus on a safe space for patients to talk about their disease and impact on their lives. Although patients report a high level of satisfaction with the listening support provided by the Wren Project, acceptability and the impact in improving people's lives including in reducing loneliness and increasing resilience has yet to be formally evaluated.

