## Progression of interventions to phase two.

In phase one, we will be evaluating various potential outcome measures for phase two whilst also ascertaining acceptability and feasibility of the three interventions to progress to phase 2. Phase two will be assessing the effectiveness of any interventions that progress to phase 2. Further selection criteria are explained below.

Interventions will only progress to phase two (effectiveness trial) if there is a high degree of acceptability and feasibility demonstrated in phase 1. Thresholds for progression to phase two are:

- 1. Green: Progress to phase 2 if >75% of phase 1 participants are satisfied/ very satisfied with the support and engaged with the support.
- 2. Amber: Consider progression to phase 2 with study team, charity, and patient group discussion, and if intervention acceptability and engagement can be feasibly improved, if between 50-75% of participants are satisfied and engaged with the support.
- 3. Red: Do not progress any intervention where <50% of participants are satisfied and engaged.

In addition, interventions that are found to not be feasible for the providers or the research team to progress to larger numbers in phase 2 will be excluded. Interventions may be trialled together for comparison or may be separate trials with separate control groups for phase two depending on phase one findings.

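### Eligibility does not screen for current or past use of the Wren Project's free listening support, so existing clients can be randomised to Wren or to control and outside use goes unrecorded

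*Protocol*

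**What the plan says.** Protocol section 6.2 (and the matching synopsis row) gives the whole of eligibility. For age it states "Both phases - Aged 18 years and over". Phase 1 then takes any INSPIRE "study participant reporting a diagnosis of SLE and requesting on the INSPIRE survey" to be considered for ADAPT. The phase 2 entry reads "Phase 2: Reporting a diagnosis of any SARD". There is no list of exclusions. Section 6.3 adds one bar linked to earlier participation: "Phase 1 participants will not be eligible for phase 2 participation".

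The synopsis says the listening arm is delivered "in line with their standard programme of offering listening support (via Zoom"). Section 5 (Listening therapy) says the charity "provides free listening support to patients with autoimmune diseases" and that its users already report high satisfaction. The synopsis entry on post-study support describes a standing group of people who have completed the programme.

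Recruitment starts from INSPIRE respondents. Only if they are too few does section 6.3 provide that "additional recruitment will be through online advertising via patient charities and support groups".

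The progression rule in section 6.1 is "Green: Progress to phase 2 if >75% of phase 1 participants are satisfied/ very satisfied with the support and engaged with the support", with Amber at 50-75% and Red below 50%.

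**The concern.** The text messages are built for the study, but the listening service exists outside it and is open to the population being recruited. Someone who is receiving it, is waiting for it or has finished it meets the criteria as written and can be allocated to any arm. The data collection in section 6.6 covers sociodemographics, the instruments, and health, social care and out-of-pocket costs. It does not name charity listening support, so the protocol would not show who had used it.

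Two results are exposed. In phase 2, the Wren-control difference shrinks if controls use the same service during follow-up, or if people in the Wren arm have little left to gain from it. In phase 1, the progression category rests on a percentage of 30 people, so a handful of previously satisfied users could move it. An analysis plan cannot repair this later, because eligibility is fixed at randomisation and exposure that was never asked about cannot be adjusted for.

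**Working it through.** **Stated totals.** Phase 1: 4 × 30 = 120. Phase 2: 100 + 100 + 300 + 300 = 800. Both match the synopsis, but only as sums. The protocol gives no alpha, power, effect size or SD, so there is no power calculation to reproduce, and it gives no number of Wren users. Every share below is an assumption.

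**Dilution in phase 2.** Let δ be the benefit of a first Wren course.

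- *Concurrent use by controls.* If a share c of controls gets the full benefit during follow-up, the difference is δ − cδ = δ(1 − c). This is an upper bound, because someone part-way through at baseline already carries some of the benefit.
- *Past use.* Randomisation spreads past users over the arms; let their share be e in each. Their earlier gain is already in their baseline, so past users in the control arm show no change. Past users in the Wren arm gain gδ from a repeat course, with g between 0 and 1. The difference is (1 − e)δ + e·gδ = δ[1 − e(1 − g)].
- *Sample size.* The factor needed to keep the same power is the inverse square of the multiplier on δ.

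| Case | Multiplier on δ | Sample factor |
|---|---|---|
| 10%, no further gain (g = 0), or c = 10% | 0.90 | 1/0.81 = 1.23 |
| 20%, no further gain, or c = 20% | 0.80 | 1/0.64 = 1.56 |
| 30%, no further gain, or c = 30% | 0.70 | 1/0.49 = 2.04 |
| 20% past users, half the gain (g = 0.5) | 0.90 | 1/0.81 = 1.23 |
| Any share of past users, full repeat gain (g = 1) | 1.00 | 1.00 |

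**Power at the provisional 100 v 300.** Assume two-sided alpha 0.05 and SD 1. The effect detectable with 80% power is (1.960 + 0.842) × √(1/300 + 1/100) = 2.802 × 0.1155 = 0.32 SD. If a share of 5%, 10%, 20% or 30% gains nothing further, power for that effect falls to 75.9%, 71.3%, 61.1% or 50.0%.

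**Progression in phase 1.** Green needs more than 0.75 × 30 = 22.5, that is, at least 23 of 30. Suppose k past users are all satisfied and engaged, and new users are so at rate r. The expected count is r(30 − k) + k, so Green needs k > (22.5 − 30r)/(1 − r).

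- With r = 17/24 = 70.8%, k must exceed (22.5 − 21.25)/0.2917 = 4.3, so 5 are needed.
- At that rate, k = 3 gives (19.125 + 3)/30 = 73.75%, still Amber. k = 4 gives 74.7%, still Amber. k = 5 gives (17.71 + 5)/30 = 75.7%, Green.
- With r = 60%, k must exceed 4.5/0.40 = 11.25, so 12 are needed.
- With r = 74%, k must exceed 0.3/0.26 = 1.15, so 2 are needed.

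The category is therefore sensitive only when new users already stand close to the threshold.

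**The case against.** Several stronger readings are tempting, and the protocol does not support them.

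- *That past users in the Wren arm liked it enough to enrol again.* Nobody enrols in Wren here. People volunteer for a randomised study with, in phase 1, a one-in-four chance of Wren, and the service is free outside it. Any upward pull on satisfaction rests on the reported satisfaction of existing users, not on self-selection into a repeat.
- *That recruitment runs through charities.* That is a fallback in section 6.3. INSPIRE respondents come first in both phases, although they are not screened for Wren use either.
- *That past users among controls shrink the difference on their own account.* Baseline is measured before allocation and within-person change is analysed, so their past benefit is already in their baseline. Dilution from past use needs a weaker gain from repeating the course.
- *That barring phase 1 participants from phase 2 is an error, or shows an exposure-control policy applied inconsistently.* The sentence is sound and no reason is given for it. The gap lies in the criteria of section 6.2.

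Other objections carry some weight. The phase 2 numbers are provisional and will be recalculated from phase 1. The charity may decline repeat clients, although they could still enter control or another arm. The baseline questionnaire is not shown and might ask about other support. Broad eligibility is also defensible where Wren is part of the background to usual care. But the protocol does not make that argument, says the service's impact has yet to be formally evaluated, and would still need exposure recorded to interpret the contrast. These points reduce the size and the urgency; they do not close the gap.

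**Conclusion.** The point holds in a limited form. As written, current and past Wren clients are eligible in both phases and can be allocated to any arm, and the protocol neither stratifies by Wren use nor plans to record it. Concurrent use by controls dilutes the phase 2 contrast directly. Past use dilutes it only in proportion to the gain lost on repetition. The sample factors of 1.23, 1.56 and 2.04 are ceilings for assumed shares of 10%, 20% and 30%, and the real share is unknown. A false Green in phase 1 would take about 5 satisfied past users among 30 if new users stood at 71%, and more if they stood lower. This is a real but unquantified weakness, cheap to close before randomisation and hard to repair afterwards.

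**What to change.** 1. Add to section 6.2, for both phases, an exclusion of people currently receiving or waiting for Wren listening support, and likewise of current attendees of the Flexifit classes for people with chronic conditions. Ask this before randomisation.
2. For past Wren users, either exclude them too, or record past use at baseline and stratify or adjust for it. If they stay in, report the progression percentages with and without them.
3. Ask participants in all arms, at both follow-ups, whether they used either service outside the trial.

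The cost is one eligibility line, one screening question and one follow-up question. The downside is a few lost volunteers and a slightly narrower population; recording past users instead of excluding them keeps that loss smaller.
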